The FDA has reviewed the study and gave an FDA IND (#145,538). Approved was also given by the research divisions of Cumberland Pharmaceuticals (Cumberland Pharmaceuticals have agreed to donate N-acetylcysteine for the study).

10) Study Design

1) The treating ED physicians (other than the investigator or coinvestigators) will identify potential subjects in the Emergency Department at Harbor UCLA via initial evaluation (standard of care) including blood draw for a standard CVA panel (CBC, Chemistries, PT, PTT, neuronal specific enolase, s100b) and brain imaging. Subjects who present with neurological deficits consistent with stroke without hemorrhage less than 24 hours since symptom onset will be asked to whether they would be interested in participation in a research in our study and if so, the treating ED physician will contact investigators or study team member. Investigators or study team member may access medical record to confirm eligibility before approach subject.

If treating physician is member a co-investigator/ study team member, s/he will approach subject about participation once deemed to meet eligibility criteria. (See inclusion and exclusion criteria below). Informed consent will be obtained for all subjects either from the subjects themselves or if they do not have capacity, from their legally authorized representative (See Section 16 below).

2) Each subject will undergo, as part of standard of care, evaluation and assessment using the National Institutes of Health Stroke Scale (NIHSS) and the Modified Rankin Scale (MRS) which have been similarly used in the European Cooperative Acute Stroke Study III, ECASS III (3). The NIHSS is a 15-item scale that measures the level of neurologic impairment. The MRS is a measure of disability with scores ranging from 0 (no symptoms at all) to 6 (death). Individuals must have an NIHSS of at least 5 to be eligible for this study. This data will be recorded for study purposes using a standard data collection sheet.

3) Subjects will receive standard of care with the study intervention being considered an “add-on” therapy. Thirty minutes after enrollment, eligible subjects will be randomized into one of two arms: placebo or NAC.

PROTOCOL TITLE: Randomized Placebo Controlled Trial of Intravenous N-Acetylcysteine for the Treatment of Acute Ischemic Stroke

Any patient receiving t-PA who enrolls in the study will have their study drug infusion delayed by 24 hours after the completion of the t-PA infusion.

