Our patients tend to be economically disadvantaged but since there are no financial incentives either for the patient or for the investigators, this bias has been minimized. Patients will receive the same care whether they participate in the study or decline.

Exclusion Criteria:

- Evidence of hemorrhagic stroke on initial CT scan
- Need for thrombectomy as determined by the treating neurologist
- Known allergy to NAC
- Protected populations, including age < 18, known pregnancy, and prisoners
- Patients who are DNR/DNI at the time of presentation with a short life expectancy

b) Local Number of Subjects

The total number of local subjects will be 117 (39 subjects with moderate stroke = NIHSS 5-15; 39 subjects with moderate to severe stroke = NIHSS 16-20; 39 subjects with severe stroke = NIHSS = 21-42)

This number was derived using a group size analysis based on previous work on oral NAC for ischemic stroke (37) and a hypothesis of finding no

difference (defined as a change in NIHSS < 4) between NIHSS scores at 90 days. With a power of 0.80 and an alpha 0.05 we would need 47 subjects in each group. Assuming a dropout rate of 25% or lost to follow-up, we would enroll 59 in each group for a total of 117.

(Group sample sizes of 47 and 47 achieve 81% power to detect a difference of 4.0 using a one-sided Mann-Whitney U or Wilcoxon Rank-Sum test assuming that the actual data distribution is normal when the significance level (alpha) of the test is 0.05 and the standard deviation is 7.4 in both groups.)

c) Study-Wide Number of Subjects

This is a single center study at the Harbor-UCLA Medical Center.

d) Study Timelines

Estimated time to complete enrollment is December 2025. Review of the neurology services revealed that Harbor-UCLA typically sees 20 patients per month that would be eligible for the study.

e) Study Endpoints

The primary study endpoint will be comparison between groups (NAC treated group versus treatment) of the NIHSS at 90 days.

Secondary endpoints include changes in the MRS, GOS, BI, and blood tests at 30 days and 90 days, as well as MRI data including changes in brain volume and gliosis at 90 days.

f) Procedures Involved in the Human Research

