First, subjects will be screened for neurological deficits consistent with cerebral vascular accident via history, physical examination and emergent evaluation in the Emergency Department which will include a noncontrast CT of the brain and an emergent Stroke Code, where our Neurology team will immediately consult on the patient at the bedside.

As part of the initial evaluation, the patient will be assessed with the National Institutes of Health Stroke Scale (NIHSS) which uses a 15-item scoring system to assess the level of neurological impairment. The items assessed include: Level of consciousness (LOC) responsiveness, LOC questions, LOC commands, best gaze, visual field, facial palsy, best motor arm, best motor leg, limb ataxia, sensory function, neglect, dysarthria, best language, extinction and inattention, formerly called neglect (31, 32).

PROTOCOL TITLE: Randomized Placebo Controlled Trial of Intravenous N-Acetylcysteine for the Treatment of Acute Ischemic Stroke

A Modified Rankin Scale (MRS) will also be obtained; The MRS is a simple scoring system that runs from 0-6, from perfect health without symptoms to death. 1- no significant disability, able to carry out all usual activities, despite some symptoms. 2 - slight disability, able to look after own affairs without assistance, but unable to carry out all previous activities. 3 - moderate disability, requires some help, but able to walk unassisted. 4 - moderately severe disability, unable to attend to own bodily needs without assistance, and unable to walk unassisted. 5 - severe disability, requires constant nursing care and attention, bedridden, incontinent.

The neurology consult team in conjunction with the Emergency Department will then make an assessment as to whether the patient is eligible to receive treatment with t-PA (based on national criteria of the American Heart Association and American Stroke Association - https://www.stroke.org/-/media/Stroke-Files/Ischemic-StrokeProfessional-Materials/AIS-Toolkit/AIS-Professional-EducationPresentation-ucm_485538)

NAC or placebo infusion will be started 30 minutes after the enrollment of the study. For subjects who receive t-PA, NAC or placebo infusion will be started 24 hours after the conclusion of the t-PA infusion.

Prior to the starting of the study medication, all subjects will receive 12.5 mg intravenous diphenhydramine to reduce the incidence of allergic reactions.

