Data from the patient examinations will be stored in REDCAP database after being de-identified. It will be stored until this study completes. The data will be shared among the principal investigator and co-investigators. Principal investigator will be responsible for receipt or transmission of the data.

i) Confidentiality

Confidentiality will be maintained by use of coded data sheets and an enrollment logbook. Data will be stored in a password locked REDCAP database. It will be stored till the completion of this study. Only research investigators and research associates will have access to this data.

j) Provisions to Monitor the Data to Ensure the Safety of subjects

PROTOCOL TITLE: Randomized Placebo Controlled Trial of Intravenous N-Acetylcysteine for the Treatment of Acute Ischemic Stroke

[name] is an Emergency Physician and Researcher located at the Lundquist Institute at Harbor-UCLA Medical Center who is not associated with the study and who will act as a Safety Monitor. Although NAC has FDA approval for acetaminophen poisoning, it does not have an FDA indication for Acute Ischemic Stroke and [name] will review the prospectively collected safety data specifically looking for adverse events (both non-serious and serious adverse events), and will also analyze each subjects' medical record which includes nursing notes, physician notes, ancillary care notes, vital signs, laboratories, clinical studies.

Since this a single hospital trial, [name] will the sole Safety Monitor and will act as an independent overseer who will access the care of each subject and the ongoing compilation of safety data throughout the trial and have the authority to modify or stop the trial at his discretion.

Tracking adverse events

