Most common side effects included drowsiness, dizziness, headache, irritability, stomach upset, vision changes (blurred vision), decreased coordination or dry mouth/nose/throat

12) Potential Benefits to Subjects

Improved functional outcomes after a cerebral vascular event.

13) Provisions to Protect the Privacy Interests of Subjects

Data confidentiality is maintained as above. Only research investigators will have access to this data.

The enrollment will be performed in the emergency department. We will not discuss private medical information in a setting with other than a health care provider or in other than a private clinical setting.

We will make sure situations such as answering sensitive questions by telephone while at home or work will not happen in this study.

We will limit the information being collected to only the minimum amount of data necessary to accomplish the research purposes.

14) Compensation for Research-Related Injury

There is no commitment to provide any compensation for research-related injury. In the event that subjects are injured as a result of participating in this research, emergency care will be available on site. Subjects will, however, be responsible for the charges for the emergency and/or inpatient care.

15) Economic Burden to Subjects

None – subjects will already be present at the hospital for care.

16) Consent Process

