If subject is deemed incapable of decision-making or unable to physically sign a consent document, consent will be sought from the subject’s the Legally Authorized Representative (as per HRP-013 SOP LARs, Children, Guardians). This individual will complete the Self-Certification of Surrogate Decision Makers form (Appendix 3) for documentation.

Study participation will be discussed with both the patient and the physician of record/primary medical providers. Patient capacity to make decisions will be determined by the primary medical providers per routine. The study team will also determine each patient’s (potential subject’s) decision making capacity for participation in the study. Patients without capacity to make decisions and who lack a surrogate decision maker will be excluded from the study. Surrogate decision makers will be informed about the study in the same way as described above and offered to provide consent for the patient to enroll in the study.

If and when a subject regains their capacity for decision-making, consent for continued participation in the study will be sought. The standard operating procedure for informed consent will be followed (SOP: Informed Consent Process for Research, HRP-090).

17) Process to Document Consent in Writing

We are following “SOP: Written Documentation of Consent (HRP-091).”

Individuals who are not yet adults, pregnant women, and prisoners will be excluded in this study. Other vulnerable subjects, such as students, subjects with limited or no treatment options, and socially and economically disadvantaged, may be included in this study. This study does not involve more than minimal risk to the subject.

18) Drugs or Devices

N-Acetylcysteine and placebo. Study drugs will be stored, handled and dispensed by an ED pharmacist who is working at the time of study enrollment.

[name]., the ED Pharmacist will maintain drug accountability logs in compliance with FDA regulations. She will instruct other ED pharmacists about the study and the randomization log which will

be kept in the pharmacy room in the ED. She will also create study drug labels to keep the nurses, physicians and patients blinded to the study medication.

19) Multi-Site Human Research

N/A

20) Community-Based Participatory Research

This is not a community-based participatory research project.

21) Sharing of Results with Subjects

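### Allocation uses neither NIHSS band nor t-PA status, both known early, in a small trial whose primary comparison states no baseline adjustment

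*Combined protocol and SAP*

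**What the plan says.** Section 18 (Drugs or Devices) has the ED pharmacist on duty store and dispense study drug. Of the lead ED pharmacist it says: "She will instruct other ED pharmacists about the study and the randomization log which will" "be kept in the pharmacy room in the ED". Labels blind nurses, physicians and patients.

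Section 10, item 3 describes allocation in one sentence: "Thirty minutes after enrollment, eligible subjects will be randomized into one of two arms: placebo or NAC". No sequence method, block size or stratification factor is given in the text available.

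Two prognostic or logistic factors are nevertheless built into the design:

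- **Severity.** Section 10(b): "The total number of local subjects will be 117 (39 subjects with moderate stroke = NIHSS 5-15", with 39 more at NIHSS 16-20 and 39 at 21-42. These are enrolment caps; they do not balance the arms inside a band.
- **t-PA.** Section 10(f): "For subjects who receive t-PA, NAC or placebo infusion will be started 24 hours after the conclusion of the t-PA infusion". The t-PA decision follows the initial neurology assessment.

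Section 10(e) makes the primary endpoint a comparison of day-90 NIHSS between groups. Section 10(b) sizes the trial on a one-sided rank-sum test. Neither mentions baseline NIHSS, band or t-PA as an adjustment.

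On timing, section 10(f) adds: "NAC or placebo infusion will be started 30 minutes after the enrollment of the study". That is the same 30-minute point that item 3 gives for randomisation.

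**The concern.** The caps force the sample to run from NIHSS 5 to 42 in three equal parts, so baseline severity will vary widely. Day-90 NIHSS is the same scale measured later, and baseline severity can be expected to predict it. If chance puts more severe strokes in one arm, the observed day-90 difference mixes that imbalance with any drug effect, and no stated analysis separates them. t-PA raises the same issue, because it also fixes when study drug starts.

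Both factors are known early, so balancing on them is feasible. The question is how large an imbalance the described scheme leaves open in a trial of 117.

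The timing statements raise a smaller, separate problem. Section 10, item 3 doses by weight, so an active bag cannot be made up before the arm is known. For subjects not given t-PA, randomisation and infusion start cannot literally share one time point.

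**Working it through.** **The plan's own figure.** Inputs from section 10(b): 47 per arm, difference 4.0, SD 7.4, one-sided alpha 0.05, Mann-Whitney test on normal data. With the rank-test efficiency 3/π:

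4 / (7.4 × √(2 / (47 × 3/π))) = 2.56; power = Φ(2.56 − 1.645) = 0.82.

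A simulation of 5,000 tests gave 0.823. The stated 81% is reproduced to within about a point. The standard error of the planned difference in means is 7.4 × √(2/47) = 1.5 points.

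**Allocation model.** Section 10(b) plans 59 per group for a total of 117, so I take 59:58, with three bands of 39 and no stratification.

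*Split within one band.* The number k of a band's 39 subjects in the 59-subject arm is hypergeometric: P(k) = C(39,k) × C(78,59−k) / C(117,59). Summing over k ≤ 14 and k ≥ 25 gives **0.050**.

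*Any of three bands.* P = 1 − Σ C(39,a)C(39,b)C(39,c) / C(117,59), over a+b+c = 59 with each count from 15 to 24. This gives **0.12**.

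Under simple coin-toss randomisation the figures would be 2 × P(Bin(39, 0.5) ≤ 14) = 0.108 and 1 − (1 − 0.108)³ = 0.29. Those need a scheme that does not hold the arms near 59:58.

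**Baseline NIHSS gap from band mix.** Band means are not in the documents. I assume 10, 18 and 26.

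- Between-band variance: 39 × (64 + 0 + 64) / 116 = 43.0.
- SD of the gap between arms: √(43.0 × (1/59 + 1/58)) = **1.2 points**.
- Probability of a gap of 2 points or more, by enumeration: **0.09**. Assumed means of 9/18/24 and 11/18/28 give 0.08 and 0.13.

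If a fraction b of a baseline gap persists to day 90 (not documented; range 0 to 1), a 2-point gap shifts the observed difference by 2b, that is 0 to 2 points against the target of 4.0.

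**t-PA.** The share receiving t-PA is not in the documents. I assume 20% and 30%.

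| t-PA subjects | SD of difference in share | P(difference ≥ 10 points) |
|---|---|---|
| 23 of 117 | 7.4 points | 0.16 |
| 35 of 117 | 8.5 points | 0.23 |

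**With stratification by band.** In blocks of four, 39 subjects make nine full blocks plus three subjects, so a band filled entirely under the scheme splits 20:19. The largest gap from band mix under the same assumed means is then (19×10 + 19×18 + 20×26)/58 − (20×10 + 20×18 + 19×26)/59 = 18.14 − 17.86 = 0.3 points. Varying block sizes would loosen this slightly.

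**The case against.** Four arguments deserve weight.

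1. *Chance imbalance is not bias.* Randomisation keeps the error rate of an unadjusted test, and random severity differences are part of the sampling error that the SD of 7.4 is meant to represent. This stands. What remains is that the plan forgoes precision it could have, and a visibly unbalanced result would be hard to read.
2. *Baseline adjustment alone would deal with most of it.* Largely true, but the plan states none. Stratifying without using the strata in the analysis would also be incomplete, so the fix needs both.
3. *Concealment.* A reader might infer that recruiters can see the next arm, since "The enrollment will be performed in the emergency department" (section 13) and the log sits in the same department. The documents do not support that. Pharmacists hold the log, consent belongs to investigators, the study team and research associates (sections 10 and 16), no section gives recruiters access to the log, and section 10(a) calls for consecutive subjects. Randomising after enrolment favours concealment. Foreknowledge is a possible risk only. It is also true that the labels protect a bag already assigned and do not conceal the next assignment.
4. *Timing.* A reader might infer that every subject not given t-PA must deviate, or that departures in the half hour use up band places. The first needs to-the-minute enforcement, which is not stated; nothing in the documents suggests the second. What stands is a clash of wording.

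**Conclusion.** The point holds as an inexpensive improvement. Allocation ignores two factors known early, and the primary comparison states no adjustment for either.

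The 5% and 12% band-split figures rest only on the planned 59:58 balance and on bands filled to 39. The figures of 11% and 29% would apply only under coin-toss randomisation and should not be quoted for balanced arms. The SD of 1.2 points and the 9% depend on assumed band means; the 16-23% depends on an assumed t-PA share. How much of a baseline gap reaches day 90 is unknown.

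The consequence is lost precision and interpretability in one small trial, not bias on average and not an invalid test. The two statements of the 30-minute point must be reconciled.

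**What to change.** 1. For subjects still to be enrolled, allocate by permuted blocks of varying size, stratified by NIHSS band (5-15, 16-20, 21-42), and by t-PA if wanted.
2. Account for the strata in the primary analysis, for example with a van Elteren test stratified by band, which keeps the rank-based approach. This can cover subjects already randomised, since baseline NIHSS is recorded for all. Specify it before any unblinded look at the data.
3. Reveal one assignment at a time, to the dispensing pharmacist only, after enrolment is recorded. Section 10(i) says "Data will be stored in a password locked REDCAP database"; if the site has REDCap's randomisation module, use that. Otherwise pharmacy can hold sequential sealed assignments for each stratum.
4. Reconcile section 10, item 3 with section 10(f) so that allocation precedes preparation of the bag. The time of infusion start is for the investigators to settle.

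**Cost.** A protocol amendment and its review, a new list part-way through the trial, a set-up task, and restricted system access for pharmacists if REDCap is used. Three strata, or six with t-PA, will leave a few incomplete blocks. Subjects already randomised keep whatever imbalance they have, so the balance gain shrinks as enrolment proceeds. No extra patients or visits are needed.
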